Phase	Phase II/III
Objectives	This study include three specific aims: Aim 1. To evaluate the short- and longer-term effectiveness of, PD alone ( PD ), PD + T-Wellness ( PDT ), and control (C, provision of child mental health and referral information). Hypotheses: (a) PD is more effective than control; and (b) PD with T-Wellness ( PDT ) is more effective for CHWs/teachers than PD alone; and (c) PDT has a more favorable cost-effectiveness ratio than PD alone; Aim 2. To examine effectiveness mechanisms and theory of change underlying the EBIs. Hypotheses: the mediational mechanisms of PD (teacher EBI strategy use as a mediator between intervention and child outcomes) and PDT (teacher stress management and EBI strategy use as mediators) will be supported; Aim 3. To examine implementation contextual factors and mechanisms that contribute to CHWs' (teachers') uptake and sustainment of EBI strategies within PD and PDT schools. Hypotheses: better fidelity, teacher mental health and more supportive contexts will be associated with better teacher uptake and sustainment of EBI strategies and more effective task-shifting.

Methodology	A cluster randomized controlled trial (cRCT), single blind and mixed-methods design will be applied. All study activities will be conducted in Uganda. Thirty-six public primary schools (18 urban and 18 rural), 540 teachers (~15 per school) and 1,980 parent-child pairs (~55 per school) will be recruited. Schools will be assigned to one of three conditions (PD, PDT, control). A stratified-block randomization procedure will be applied to ensure approximately similar characteristics across study regions and conditions.
Endpoint	Effectiveness outcomes will be assess 3 times (Time 1= before intervention; Time 2= immediate after PD/PDT intervention; Time 3= 12 months after Time 2). The primary teacher effectiveness outcomes (or intermediate effectiveness outcomes) are teachers' EBI strategy use and teacher stress management. The primary child effectiveness outcomes are child externalizing and internalizing problems (mental health outcomes). The secondary child effectiveness outcomes are emotion regulation, executive functioning (ability for cognitive processes that are foundation for the cognitive control of behavior), and social relationship (student-teacher relationship, peer relationship).

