Study Duration	This is a four-year study. Year 1 will be focused on study preparation (including conducting user-centered testing for the T-Wellness package and finalizing the PDT contents), developing implementation partnership, and capacity building for the PD/PDT implementers (Trainers from Teacher Training Colleges/TTCs and mental health institutions). Years 2-4 are intervention implementation, evaluation data and cost-benefit data collection, and data analyses.
Participant Duration	Participation duration will be varied by types of participants. 

• The intervention implementers (TTC trainers and mental health professional trainers) will participate in study for 4 years.

• Teachers participants for the T-Wellness Package User-centered & Optimization testing will participate in the study for 6 months (during Year 1 preparation only).

• Primary school teachers and selected school leadership staff (Head teacher, PTA leaders) will participate in the evaluation study for 2 years. Teachers (i.e., pre-primary and primary 1st to 4th grade, serving students between the ages of 3 and 10 years) and PTA leaders are the primary targets of the PD/PDT.

• Children and caregivers will participate in the evaluation study for 18 months.

• 

Duration of behavioral intervention	Intervention schools' teachers (pre-primary to 4 th grade teachers) and representative PTA leaders will participate in PD (3 days) or PDT workshop (4 days) in their regional Teacher Training College (TTC) during their 1st year of participation and before the 1st school term. Following the workshop training, they will also receive 8 sessions (12 hours) of face-to-face group-based coaching during the 1st and 2nd terms. For the teachers in the PDT group, additional stress management group coaching activities will also be integrated (3 additional monthly 1-hr wellness sessions for teachers as a group in each school).

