Description of Study Intervention/Procedure	

• Prior to the RCT study (or during Year 1), T-Wellness Package (a brief teacher stress management psychoeducation package, adapted from EBIs and including a half-day workshop for common stress management and a half-day for burnout management, and three follow-up group support sessions) will be tested to insure user-centeredness. we will recruit 4 study schools and applying factorial design to test the effect of each component (1 Common Stress management; 1 Burnout Stress management; 1 Combined Common and Burnout Stress management; 1 control; with ~15 teachers in each condition). Both groups' will also receive 3 post-workshop group support sessions. We will compare pre-post differences on teacher stress management and mental health using a mixed-methods data collection.

• To implement PD/PDT using a scalable approach, we will formalize partnership with the Ugandan Ministry of Education (MOE), Ministry of Health (MOH), academic medical center, and Teacher Training Colleges (TTCs) stakeholders in Year 1. The partnership and intervention implementation team will receive training from NYU PD trainers, and implement PD/PDT in Years 2-4.

• To study effectiveness-implementation aims (Aim 1-3), a cRCT will be conducted. Public primary schools from Kampala/urban and Hoima/ rural will be recruited. A stratified-block randomization procedure will be applied to ensure approximately similar characteristics across geographic regions and three intervention conditions (PD, PDT, and control). Teachers from the PD will receive a 3-day training, and teachers from the PDT will receive a 4-day training. Both intervention groups will receive 8 group-coaching sessions (with teachers from their own school). Teachers from the control schools will receive child mental health promotion materials. They will receive T-Wellness in Year 4 after the evaluation study is completed. Given the large numbers of students in schools, research staff will randomly select 10% of students and families from each school for participation in the evaluation study. A total of 1,980 families (parent-child pairs) from 36 schools (averaging 55 families/per school) will participate in the evaluation study. Effectiveness outcomes will be assessed at 3 time points over 18 months (baseline/T1, post-PD or PDT, 5-6 month/T2, and 16-18-month follow-up/T3). Objective observation, implementers, school staff, parent, and child report data (quantitative and qualitative) will be gathered.

• To study underlying mechanisms, we will use the evaluation data describe above to examine whether intervention effects on children's mental health outcomes is mediated through improvement on teachers' EBI practices (primary) and teacher stress coping. To study moderation mechanisms, geographic region, fidelity (including adherence, quality of program implementation, engagement, exposure) and other implementation contextual factors (i.e., EBI fidelity, school climate), guided by the Consolidated Framework for Implementation Research, will be studied.

• Identifiers will be removed from the identifiable survey and field notes. Data may be used for future research studies or shared with other researchers and we will not request additional informed consent from you to use these specimens as we have noted here.

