## 1.2 **Rationale**

This study involves efforts to advance the science of prevention in early childhood mental health in low-resource communities. We will investigate the effectiveness, practical implementation strategies, and underlying mechanisms of the *PD* in urban and rural Uganda. We will compare effectiveness of two *PD* implementation approaches (with and without T-Wellness) using a hybrid effectiveness-implementation CRCT. **Figure 3** shows the conceptual model for *PD* and *PDT* Theory of change in LMIC contexts, which considers *intermediate intervention effectiveness outcomes* (teacher EBI practice) and *distal effectiveness outcomes* (including primary child mental health outcomes and secondary child behavioral outcomes, defined in Table 2). *PD* is expected to change teachers' EBI practices; and the impact of *PD* on distal child mental health outcomes will be mediated primarily through changes in teachers' practice of EBI strategies. Similarly, we expect that *PDT (PD+T-Wellness)* will also have impact on distal child mental health outcomes, and this will be mediated primarily through improvement in both teachers' EBI practices/behaviors and teachers' stress management skills (cognitive and behavioral control/ coping of stress). We anticipate *changes in child behaviors will be observed in the secondary outcome domains before the mental health outcomes* (primary distal outcomes). Because *PD/PDT* will be implemented in diverse contexts, our theory of change also considers moderators from aspects of the Consolidated Framework for Implementation Research (CFIR), which proposes that five domains of contextual factors can impact effectiveness-implementation. Specifically, we expect that certain *individual, intervention implementation, and school contexts* may also influence (or moderate) intervention effectiveness. We consider geographic region (urban/ rural) as the primary moderator, and other CFIR factors listed in the figure as secondary moderators. This theory of change has been partially tested (constructs in 'red' in Figure 3) and supported in previous *PD* studies. This study will formally examine the cost-effectiveness and test the *PD/PTD* theory of change with a larger diverse sample and using scalable approaches. We select a foreign low-resource country as our study site because it provides an ideal setting to test how a mental health system can be strengthened through careful consideration of strategies while simultaneously examining effectiveness outcomes of an EBI. Also, Ugandan context is similar to other underserved and under-resourced communities in the US and other LMICs. Therefore, knowledge generated from our study will be relevant globally.

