##### **Recruitment and Referral Sources:**

- Intervention Implementer/ Trainer: Drs. [name] and [name] We will work with TTC and, MOE, and MOH to finalize the referral and recruitment process. Trainers will be identified and invited to participate. Participation will be completely voluntary, with no consequence for opting out of participation due to personal reasons.
- Schools: We will work with Ministry of Education (MOE) to finalize the referral and recruitment procedure. In general, public primary schools in targeted districts will be identified from governmental school lists in two study districts (urban and rural) provided by MOE. Principals of these schools will be invited to attend one of the information sessions hosted by the Ugandan intervention implementation team. During the recruitment session, principals will be provided with details of study requirements and intervention. They will have an opportunity to ask questions and also complete a questionnaire that seeks to gather information on school demographics, commitment to remain in a randomized condition, willingness to facilitate data collection, and allocate staff time to participate in the study. Eligible schools will be selected based on school leaders' and principals' expressed of interest and their agreement to allow teachers' voluntary participation. To ensure approximately similar characteristics in the intervention and control conditions, a statistician, unfamiliar with study schools, will match schools on size (i.e., number of teachers and students), location (urban/rural), and quality/performance from the eligible school list. A stratified-block randomization design will be applied. We will work with MOE to finalize a systematic approach to select the final 36 schools.

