Contextual Moderators (Pre/T1 and Post PD training, and during PD implementation)	a) Outer setting: Urban/rural region (Primary moderator) b) Fidelity: 4 PD/PDT measures (F, T) c) Inner setting: School EBI climate (e.g., work environment, team work alliance, leadership) (T); d) Individual/Teacher characteristics (e.g., EBI readiness/attitude; wellness) (T) e) Intervention characteristics: Acceptability; Appropriateness (T) f) Processes: Partnership Quality (e.g., TTC and teacher/PTA partnership) (T)	b) 4 Fidelity measures  (1) Adherence (F) (deliver the core content): PD/PDT Fidelity Checklists (completed after each training day & coaching session) (2) Quality of implementation (T) (Teacher Satisfaction (T) (post PD training and T2) ( $\alpha=.72$ )  and ratings of Coaches' competence); (3) Engagement (T) Strategy Knowledge  (T) (EBI knowledge gain before-after training) (test-retest $r=.35-.43$ )  ; (4) Exposure (F): Attendance tracking  ; C) School Environment Survey  ; Organization Climate Questionnaire ( $\alpha=.65-.85$ )  d) Teacher demographic  ; PHQ-mental health  ; EBP Attitude Scale  ; e) Applied Mental Health Research Dissemination and Implementation Measurements (AMHRG)  ; f) Partnership Questionnaire 
Demo (T1)	Family/Student Demo (e.g., parenting, well-being) (P)	Family: Demo  ; Parent EBI Practices (P) ( $\alpha=.69-.80$ )  ; PHQ ( $\alpha=.90$ ) 
PD/PDT Cost	Program implementation costs;	Implementation costs: actual program costs (with & without monitoring cost) 

**Note.** For **child effectiveness outcomes**, primary data source is parent-report (P); and secondary data source is child-report/testing (C). For **teacher effectiveness outcomes**, primary data sources is classroom observation (O) & teacher report (T); and secondary data source is Parent (P) report. **CFIR contextual data** will be gathered from Training/coaching session tracking data from facilitator report (F) and teachers-report (T). **Suicidal behaviors** are NOT included because this study focuses on preventive intervention and young children (ages 4-10 years). The measures used in young children usually do not include suicidal items. However, parent, teacher, and child reported depressive symptoms will be included.

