## **14 Study Administration**

### **14.1 Study Leadership**

The study team includes implementation research leadership teams from the US and Uganda. The leadership teams are to collaborate with Ugandan Ministry of Education (MOE) and Ministry of Health (MOH) to develop

infrastructure, and to coordinate, integrate, monitor, implement, and disseminate knowledge related to ParentCorps-Professional Development (PD) across sites. Overall, the US research-clinical team (lead by [name]) will work closely with the Ugandan Research-Policy-NGO leadership team to set-up a system to support PD implementation and evaluation. The US team will also work closely with Ugandan leadership team on research administrative activities, design, data analysis, report writing, and result dissemination. The Ugandan Research-Policy-NGO Leadership team (lead by [name]) will work closely with Ugandan MOE, MOH, and AfriChild leadership and will play leadership roles in: 1) developing and training localized implementation teams in urban and rural sites that include Teacher Training College (TTC) Principals, TTC teacher trainers/PD trainers, and mental health professional (MHP)/psychiatric medical officer; 2) developing and training independent research monitoring/evaluation teams in urban and rural sites that include Research Directors, data collection Research Assistants (RAs), and independent classroom observers; 3) working with local PD implementation teams from Advisory Boards (one in Urban and one in Rural region) to facilitate regulate Advisory Board meetings (3 times a year) in order to gain guidance related to program improvement, outcome interpretation and result dissemination; 4) providing oversight for all team management and effectiveness study activities; 5) facilitating knowledge sharing and learning collaboration between urban and rural sites; and 6) collaborating with the US team on design, data analysis, report writing, and result dissemination. For Implementation and effectiveness study, two site teams with parallel structure will be established- one for urban site, and the other for rural site. For each site, there will be a PD Implementation Team that leads by the TTC Principal, and an Independent Research Evaluation Team that leads by a Research Director. The TTC Principals from each site will work with Ugandan Research-Policy-NGO leadership team to recruit and train PD trainers (including two TTC Trainers/PD implementers, and one mental health professional or senior psychiatric nurse). The Research Director from each site will work with the Ugandan leadership team to recruit and train 5 part-time RAs and 2 independent classroom observers. They will not involve in any implementation activities (to maintain blind to study conditions). Both local Implementation team and Research Team will also work with the Ugandan Leadership Team to set-up Advisory Boards and conduct regular Advisory Board meetings. The Central Leadership team will also set-up regular cross-site meetings (or conference calls) for two cross-site teams to share knowledge and research/practice strategies.

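### The primary moderator, urban/rural region, is one district per setting with its own delivery team, so its interaction test can show only a difference between two sites

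*Combined protocol and SAP*

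**What the plan says.** Section 1.2 states: "We consider geographic region (urban/ rural) as the primary moderator". Table 2 in Section 6.1 repeats this under the contextual moderators, as "a) Outer setting: Urban/rural region (Primary moderator"). The same table lists fidelity (including ratings of coaches' competence) and partnership quality as separate moderators.

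Schools are drawn from "governmental school lists in two study districts (urban and rural) provided by MOE" (Section 4.4, Recruitment and Referral Sources). The Protocol Summary names the two areas: "Public primary schools from Kampala/urban and Hoima/ rural will be recruited". It gives the size as "Thirty-six public primary schools (18 urban and 18 rural), 540 teachers (~15 per school) and 1,980 parent-child pairs (~55 per school").

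On delivery, Section 14.1 sets up two parallel site teams, "one for urban site, and the other for rural site". It adds: "For each site, there will be a PD Implementation Team that leads by the TTC Principal, and an Independent Research Evaluation Team", the latter under a Research Director with that site's own assistants and classroom observers. According to the Protocol Summary, teachers attend the PD or "PDT workshop (4 days) in their regional Teacher Training College (TTC").

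For the analysis, the Aims 3 plan in Section 9 takes the Aim 1 mixed model and adds the moderator and its interaction with intervention. A significant interaction on a teacher outcome leads on to mediation-moderation models. There is no team term, and nothing limits how a regional difference is to be read.

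**The concern.** Each setting is represented by one district, one implementation team and one regional training college. Those trainers deliver the training and coaching to every intervention school in that setting. If one team trains or coaches better than the other, the PD effect will be larger at that site, and the planned model will show this as a region-by-intervention interaction. Under the label in Table 2 it would be reported as an outer-setting effect.

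Region is the primary moderator, and Section 1 presents the trial as evidence on how the programme carries across diverse contexts. A claim that PD works better in urban or in rural schools would bear on scale-up, yet a difference between two small groups of trainers would produce the same result. The Aims 3 plan could also carry the label into mechanism claims, because a significant interaction triggers further modelling.

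**Working it through.** **No stated figure to reproduce.** The documents give no alpha, power, ICC or detectable difference for the moderator test. Only the counts can be checked, and they agree: 36 × 15 = 540 teachers and 36 × 55 = 1,980 pairs. (Section 11.3 mentions 16 urban and 16 rural schools; I use the 18 and 18 of the Protocol Summary. The aliasing does not depend on this.)

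**Step 1: aliasing.** Take 36 schools, 3 arms and 2 sites. With 18 schools per site and 12 per arm, balance within site gives 6 schools per cell.
- Columns for intercept, two arms, region and two region-by-arm terms: 6 columns, rank 6.
- Adding team and two team-by-arm terms: 9 columns, rank still 6.

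The team columns duplicate the region columns, so this result needs no numerical assumption. No section moves trainers between sites or adds a second district per setting. The cross-site meetings in Section 14.1 share knowledge, not staff.

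**Step 2: which team differences enter the interaction.** The contrast is (PD − control in Kampala) − (PD − control in Hoima).
- A delivery team acts only in intervention schools, so a difference between the delivery teams goes straight into the contrast.
- An assessment team works in all arms. If its scores are shifted by the same amount in every arm at a site, the shift cancels. It matters only if it differs by arm, for example in sensitivity, scaling or loss of masking.

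**Step 3: illustrative size.** From the documents: 55 children per school. Following from them if arms are balanced within site: 6 schools per arm per site. Assumed, with no source in the documents: two-sided 5% test, ICC 0.05–0.10, baseline (T1) correlation 0.5 (variance factor 1 − 0.5² = 0.75), and between-team SD of the PD effect τ.

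Var(site × arm) = 4 × 0.75 × [ICC + (1 − ICC)/55] / 6
- ICC 0.05: 0.5 × (0.05 + 0.95/55) = 0.0336, SE = 0.183 SD
- ICC 0.10: 0.5 × (0.10 + 0.90/55) = 0.0582, SE = 0.241 SD

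With two independent teams and no urban/rural effect, the true variance is SE² + 2τ², while the test uses SE. Rejection = 2Φ(−1.96 × SE / √(SE² + 2τ²)).

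| τ | ICC 0.05 | ICC 0.10 |
|---|---|---|
| 0 | 5% | 5% |
| 0.05 | 6.7% | 6.0% |
| 0.1 | 12.1% | 9.1% |
| 0.2 | 28.6% | 20.3% |

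**Sensitivity.**
- Without baseline adjustment, over ICC 0.02–0.15, rejection runs from 14% down to 7% at τ = 0.1 and from 34% down to 14% at τ = 0.2.
- For teacher outcomes (15 per school in place of 55, other inputs as in the table), SE is 0.24–0.28, with rejection of 8–9% at τ = 0.1 and 17–21% at τ = 0.2.

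**The case against.** **The local team is part of what is tested.** Hypothesis (a) in Section 2 concerns PD delivered through localized approaches, and Section 3.1 builds a separate structure in each region. On that reading, team and region form one package. This supports a site comparison. It does not rescue the urban/rural label, because Table 2 lists fidelity, coach competence and partnership quality as moderators distinct from outer setting. The plan treats delivery and setting as different things that its design cannot separate.

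**Team variation may be small.** Trainers share preparation from the US team, there are several per site, fidelity checklists are completed throughout, and the sites meet. All this may reduce τ, and nothing in the documents says how large τ is. A τ of 0.2 equals the lower end of the 0.2–0.4 benchmark in Section 9, so the 20–29% row is a severe case; at τ = 0.05 the excess is one or two percentage points. The objection stands against the size of the illustration. It leaves the aliasing untouched.

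**Fidelity data could explain a site gap.** They can describe one, but control schools have no fidelity and there is one team per setting, so they cannot break the aliasing.

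**Stronger readings a reader might infer.**
- That the result is bound to be misread. This is a prediction; the documents show only a label without a caveat.
- That the assessment teams are as serious a problem as the delivery teams. Step 2 shows otherwise, and Section 6.1 masks family and observation assessors to condition.
- That formal moderation claims should be confined to baseline measures varying within site. That would drop planned moderators such as fidelity, for which the aliasing gives no reason.

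**Conclusion.** The concern holds as a limit on interpretation. Region and delivery team are fully aliased by design, whatever the ICC or τ. The region-by-intervention test remains a valid test of whether effects differ between the Kampala and Hoima sites. It cannot support a statement about urban or rural setting as such.

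A reader might infer that the trial's main results are compromised. They are not: Section 4.4 matches schools on location and randomization is stratified, so the Aim 1 arm comparisons are made within both sites and are unaffected. No stated decision rule depends on the regional test.

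How often a team difference would pass for an urban/rural effect depends on assumed inputs. Over τ of 0.05 to 0.2 and ICC of 0.05 to 0.10, the rate is about 6% to 29% against a nominal 5%. This shows the direction and possible scale; it is not an estimate for this trial.

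**What to change.** In Section 1.2, Table 2 and Section 9:
- Define the primary moderator as study site (Kampala versus Hoima, each including its local delivery team).
- Keep the site-by-arm test, and report arm effects by site with confidence intervals and with fidelity by site alongside.
- State that a site difference will not be attributed to urban or rural setting as such, including in any mediation-moderation model that follows from it.
- Leave the other planned moderators, fidelity included, as they are.

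This is a change of wording and reporting only, with no new schools, staff or data. The price is that the trial gives up a general urban/rural moderation claim. Recovering that claim would require several districts or teams per setting, or trainers who work in both.

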
For study implementation moderation mechanisms, the selected key moderators from the 5 CFIR domains include target individuals’ characteristics (teachers and children), school, and intervention implementation contexts will be studied (listed in Table 2). Most CFIR measures have been validated in our previous *PD* pilot trial. *PD/PDT* implementation fidelity will be assessed, characterized, and examined for moderation effects (on teacher effectiveness outcomes). Four fidelity measures will be considered, including *adherence* (the extent to which the TTC trainers deliver the core intervention content and as per program guidelines), *quality of program implementation* (assessed based on teacher satisfaction with the *PD/PDT* and ratings of TTC Coaches’ competence); *engagement* (assess trainees’ level of *PD* knowledge improvement from pre- to post-training); and *exposure* (measured by attendance of *PD* and coaching sessions).

To have a more comprehensive understanding of possible mechanisms, we also plan to conduct qualitative interviews, which will purposively select *PD* trainers (n=8), teachers (n=40; 20 from intervention and 20 from control across two sites) and our Advisory Board members, and conduct interviews at 4 time points (T1, T2, T3,

and Year 4). Interview guides will comprise semi-structured questions relating to experience with *PD/PDT*. Participants will also be asked to provide a narrative account of partnership approaches, efforts to implement *PD/PDT*, including barriers and facilitators experienced. The group interview guides will be adapted from our previous pilot *PD* implementation studies.

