## 9 Statistical Considerations

**Data Analysis Plan for Aim 1.** Prior to any outcome analyses, we will generate summary statistics for all data, summarizing with means and standard deviations for continuous variables and frequencies for categorical variables. The distribution of study variables and missing data patterns will be inspected. To estimate effectiveness, we will apply intention-to-treat (ITT) analyses and first focus on between-subject comparisons of intervention vs. control (comparing *PD* to control, comparing *PDT* to control, and comparing *PD* to *PDT*). We will estimate the impact of *PD* on children and teachers post-intervention (T2, 4-5 months after T1) and at one-year follow up (T3, 18 months after T1, or 12 months after T2). **Figure 4** below describe the model to be tested under Aim 1. School and class nesting will be considered, and a multiple imputation strategy will be applied to account for missing data. Linear mixed effect models, using SAS PROC MIXED, will be applied to examine short and longer-term impacts. We will first examine the immediate impact by modeling post-intervention outcomes (T2) as a function of intervention, adjusting for T1 outcome measures. The model accounts for between-subject (within-school and -class) correlation by including school- and classroom-level (when appropriate) random intercepts. The outcomes will be modeled as:  $Y_{ij} = \beta_1 I_j + \beta_2 C + \beta_3 X_{ij} + \gamma_j + \gamma_k + \epsilon_{ijk}$ , where  $Y_{ij}$  is the outcome for the student  $i$  in school  $j$ .  $I_j$  is intervention status (a categorical variable, with 3 levels) for school  $j$ , representing two dummy variables (control as the reference).  $C$  is the cohort indicator for

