**Figure 5. Aim 2 PD and PDT Mediation Mechanisms**

**Data Analysis Plan for Aims 3.** For moderation model testing, we will apply similar approaches as in Aim 1 and add the moderator and moderator-by-intervention interaction terms in the analysis. Figure 6 below describes the model to be tested under Aim 3. For models with a significant moderator-by-intervention term on teacher effectiveness outcomes, we will then further test mediation-moderation mechanisms by expending the mediation model described above. These methods have been utilized in our previous studies.

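### Engagement is defined as a knowledge gain and the Aim 3 model has no term for starting knowledge, so teachers who already know the strategies tend to score as less engaged

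*Combined protocol and SAP*

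**What the plan says.** Section 6.1 lists four fidelity measures: adherence, quality, engagement and exposure. Engagement is to "assess trainees’ level of *PD* knowledge improvement from pre- to post-training". Table 2 gives the instrument as a strategy knowledge test and describes the score as "EBI knowledge gain before-after training) (test-retest" r = .35-.43. Neither place gives a scoring rule, such as a simple difference or a residualised gain.

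Section 6.1 says fidelity will be "examined for moderation effects (on teacher effectiveness outcomes"). The Aim 3 hypothesis in the Protocol Summary is that "better fidelity, teacher mental health and more supportive contexts will be associated with better teacher uptake and sustainment of EBI strategies". For the model, the Aim 3 paragraph of section 9 takes an approach like that of Aim 1 and will "add the moderator and moderator-by-intervention interaction terms in the analysis". The Aim 1 model is specified as "adjusting for T1 outcome measures". It also carries a cohort term and random intercepts. Pre-training knowledge appears in none of these models. Section 1.2 makes region the primary moderator and the other contextual factors secondary.

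**The concern.** A difference between two imperfectly correlated scores carries the first score with a negative sign. A teacher who starts high, through real knowledge or through luck on the day, has a smaller expected gain than one who starts low. If the gain is labelled engagement and the starting score is left out of the model, two different things are mixed: how much the teacher took from the training, and how little the teacher knew before it.

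Teachers with good prior knowledge may also use the strategies more. Their low engagement scores would then work against the hypothesised positive association. The trial could report that engagement matters little when the scoring is part of the reason. There is a further consequence in section 9: mediation-moderation models follow only where the moderator-by-intervention term is significant, so a weakened term could also stop the follow-up analysis.

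**Working it through.** **Inputs.** From Table 2: test-retest r = .35 to .43. The documents give no data from which to reproduce this figure. They also omit the retest interval, whether training fell between the two tests, and the pre and post SDs. Assumptions: the stated r approximates the pre-post correlation in this trial, and k = SD(post)/SD(pre) lies between 0.5 and 2.

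**Step 1: gain against starting score.**

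corr(gain, pre) = (rk - 1) / sqrt(1 + k² - 2rk), which equals -sqrt((1 - r)/2) at k = 1.

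| k | r = .35 | r = .43 |
|---|---|---|
| 0.5 | -0.87 | -0.87 |
| 1 | -0.57 | -0.53 |
| 1.5 | -0.32 | -0.25 |
| 2 | -0.16 | -0.08 |

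At k = 1 the arithmetic is -sqrt(0.65/2) = -0.570 and -sqrt(0.57/2) = -0.534. The squares are 0.325 and 0.285, so 29-33% of the variance of the gain is shared with the starting score. Over the whole range of k the shared variance runs from about 0.6% (0.077²) to 76% (0.87²). The correlation reaches zero only at k = 1/r, that is 2.86 or 2.33.

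**Step 2: what this does to individual teachers.** In a bivariate-normal simulation with equal SDs, 50-52% of teachers in the top quartile of starting knowledge fell in the lowest quartile of gain, and 5-6% in the highest. The pattern was mirrored for the bottom quartile.

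**Step 3: what this does to the engagement slope.** Suppose uptake = a × post + b × pre + error, with equal SDs set to 1.

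- cov(uptake, gain) = a(1 - r) - b(1 - r) = (a - b)(1 - r)
- var(gain) = 2(1 - r)
- slope on gain alone = (a - b)/2

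With b = 0 the slope is half of a. With b = a it is zero. It is negative only if b exceeds a. With unequal SDs the crossing point moves: for standardised coefficients, the sign changes when b(1 - rk) exceeds a(k - r).

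If uptake depends on post-training knowledge alone, the gain correlates with uptake at a fraction corr(gain, post) = (k - r) / sqrt(1 + k² - 2rk) of the strength of the post-training score. That fraction is 0.53-0.57 at k = 1 and 0.08-0.87 over k = 0.5 to 2. It is always positive.

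**Step 4: with the pre-score in the model.** c × gain + d × pre = c × post + (d - c) × pre. The coefficient c is the same whether gain or post-score is used, and in the Step 3 model it equals a whatever b is.

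**Step 5: reliability.** If r is read as the reliability of the test, the reliability of the gain at equal SDs is (r - p)/(1 - p), where p is the observed pre-post correlation. This gives .35-.43 at p = 0, .19-.29 at p = .2, and 0 when p equals the reliability.

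An illustrative simulation assumed that engagement raises both post-training knowledge and practice by 0.3 per SD. Practice correlated 0.27-0.29 with true engagement and 0.07-0.08 with the simple gain. The slope on gain was 0.065-0.075 unadjusted and 0.09-0.27 with the pre-score added. It was 0.09-0.10 when true baseline knowledge had no effect on practice, and higher as that effect grew. The increase is not recovered engagement: a noisy pre-score only partly controls for true knowledge.

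**The case against.** **The scoring rule is not written down.** This stands. A reader might infer that the plan prescribes a raw difference. It does not: a residualised gain is also compatible with the wording, and the note to the timeline table lists fidelity procedures among items to be finalised. But a simple difference is what gain and improvement ordinarily mean, and nothing in the plan points to another rule.

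**The size rests on inputs that the documents do not give.** This stands too. A reader might take 29-33% as the size of the problem. It is one point in a range of about 0.6% to 76%. What does not depend on the exact SD ratio is the sign, which is negative throughout k = 0.5 to 2.

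**Baseline adjustment already covers the path.** Partly. For teacher outcomes the T1 covariate is baseline EBI practice. To the extent that prior knowledge acts through existing practice, it is already conditioned on. Knowledge not yet reflected in practice is left uncontrolled.

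**Adding the pre-score does not cure a noisy test.** Correct, as Step 5 shows. The adjusted coefficient describes post-training knowledge given measured starting knowledge, not engagement free of error.

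**Conclusion.** The point holds as a cheap improvement to one measure. If engagement is scored as a simple difference, it is negatively coupled to starting knowledge: about -0.53 to -0.57 at equal SDs, taking the stated r as the pre-post correlation, and -0.08 to -0.87 over SD ratios of 0.5 to 2. The main expected effect is attenuation of the engagement-uptake association. Its size in this trial cannot be computed from the documents.

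Three stronger conclusions a reader might draw are not supported:

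- That the best-informed teachers are always scored least engaged. It is a tendency: at equal SDs about half of the top starting quartile fall in the lowest gain quartile.
- That the association will be reversed. At equal SDs this needs prior knowledge to matter more for uptake than post-training knowledge, and nothing in the documents shows that.
- That the Aim 3 result as a whole is distorted. Engagement is one of four fidelity measures, all secondary moderators. Adherence, quality and exposure do not use this score.

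**What to change.** In section 6.1, Table 2 and the Aim 3 paragraph of section 9:

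- State how the knowledge gain is scored.
- Wherever engagement enters a moderation or mediation-moderation model, add the pre-training knowledge score as a covariate. Keeping the gain or replacing it by the post-training score makes no difference to the engagement coefficient once the pre-score is in.
- Wherever engagement-by-arm is tested, add pre-score-by-arm as well. Otherwise the interaction keeps the same dependence on starting knowledge.
- State that the low reliability of the test remains a limitation, so a null engagement result is weak evidence that engagement does not matter.

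The cost is one degree of freedom for the covariate and a second where the interaction is added. Both scores are already needed to form the gain, so no new data are collected.
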